Overall, the BG505 SOSIP.664 with 3M-052-AF was generally well tolerated, with no unsolicited Grade 3 or 4 AEs, no related SAEs, AESIs, or deaths, and no unplanned study pauses. Other than the persistent erythema in one of the HVTN

137 Part A Group 2 participants described above, all reactogenicity symptoms resolved within 14 days and generally within 7 days. For more detailed information, please see the IB.

HVTN 300 (NCT04915768): This study is a first-in-human, unblinded trial testing a 300 mcg dose of a CH505 TF chTrimer (a stabilized, chimeric SOSIP Env trimer) in combination with a 5 mcg 3M-052-AF + 500 mcg Alum delivered via split injection into both the right and left deltoids. The planned schedule is 5 total vaccinations at months 0, 2, 4, 8, and 12.

As of September 7, 2022, the study is ongoing and all 13 participants have received the first vaccination, 10 participants have received the second vaccination, 9 participants have received the third vaccination, 9 participants have received the fourth vaccination, and 6 participants have received the fifth vaccination. Five participants have discontinued further vaccinations, 1 due to a panic attack after the first injection (this participant had a history of panic attacks before being part of the study), 3 due to reactogenicity events, and 1 was lost to follow-up. Out of these 5, 2 terminated from the study early (panic attack and lost to follow-up) and 3 have remained in the study for follow-up.

All participants experienced at least some local reactogenicity during the trial, mostly mild to moderate. One (1) participant experienced severe pain/tenderness in both the right and left injection sites 3 days following the fourth vaccination, though it lasted only one day.

All participants reported some systemic reactogenicity during the course of the trial to date, mostly mild to moderate. For example, 11 of 13 participants experienced systemic reactogenicity after the first dose. Five (5) participants reported Grade 3 (severe) systemic reactogenicity during the trial through September 7, 2022. One (1) of these 5 participants received a subsequent vaccination without any Grade 3 reactogenicity, one (1) experienced an additional Grade 3 systemic reactogenicity symptom, one (1) has not yet received a subsequent vaccination, and two (2) declined to receive additional vaccinations after their first Grade 3 systemic reactogenicity event. All Grade 3 events resolved within the 7-day reactogenicity period; the longest duration for severe reactogenicity was 2 days.

There have been no related SAEs, AESIs, or deaths as of September 7, 2022.

2.5 Rationale for Schedule

Previous trials of DNA vaccines for HIV-1 Env immunogens have used a 0-, 1-, 3-, and 6-month vaccination schedule, exactly as proposed in this study. Those regimens were well tolerated and immunogenic (12, 27). Specifically for ID delivery, both Abs and T-cell responses were induced (25, 26). In HVTN 098, the fourth vaccination boosted the magnitude of total Ab response for all treatment

groups against gp140 antigens from clade A and B as compared to the magnitude of total Ab response after the third dose (25).

[figure not shown]

Figure 2-4 IgG binding antibody responses as measured by binding antibody multiplex assay (BAMA) against consensus Env gp140 antigens for clades A, B and C. Assays were performed 2 weeks after the third and fourth vaccinations and 6 months after the fourth vaccination. Positive responses are shown in filled circles in color, negative responses are shown in open gray triangles. Box plots represent the distribution for the positive responders only. Bar plots show response rates. Numbers below the bars indicate numbers of positive responders and total participants. Positive response rates were compared using the Fisher's exact test for unpaired data (between treatment groups) and the McNemar test for paired data (between visits). Response magnitudes among positive responders were compared using the Wilcoxon rank sum test for unpaired data and the Wilcoxon signed rank test for paired data. All p-values are two-sided. False-discovery rate adjusted q values were calculated to account for multiple antigens, multiple timepoints, or treatment groups (Figure from supplemental data (25)).

By including 2 boosts of Trimer 4571 at months 3 and 6 in Group 2, we can assess whether additional doses of protein and DNA lead to enhanced

immunogenicity compared to DNA alone in this study (Group 1) and previous studies. By maintaining a standard schedule, data will be directly comparable to previous DNA vaccine studies.

2.6 Rationale for Dose of Trimer 4571 and 3M-052-AF + Alum adjuvant

The ongoing and completed clinical trials with Trimer 4571 are listed in [Table 2-2](#). Data on the safety and immunogenicity of Trimer 4571 + Alum from VRC 018 is available. No related SAEs were reported. The immunologic assays and analysis for this study are ongoing. Trimer 4571-specific Ab titers in serum samples were measured by Electrochemiluminescence (ECLIA) using a Meso Scale Discovery (MSD) platform at baseline and at 2 weeks after the third product administration. Both the 100 mcg (n = 3) and 500 mcg (n = 5) doses elicited Trimer 4571-specific Abs, with geometric mean AUCs 8-fold and 40-fold over background, respectively. No substantial difference was observed between the 100 mcg and the 500 mcg dose, so the 100 mcg dose will be tested in this trial.

For additional information, see the IB.

Table 2-2 Clinical trials with Trimer 4571

Study	ClinicalTrials.gov NCT # / Study Status	Participant HIV status	Number receiving Trimer 4571 + Alum	Route / Dose	Schedule	Safety data (ClinicalTrials.gov)
VRC 018	NCT03783130 / Completed	Negative	16	IM or SC at 100 or 500 mcg Trimer and 500 mcg Alum	0, 2, 5 months	As of August 2021, final study data: no related SAEs, related grade 4 AEs, or related MAAEs were reported or other unexpected reactions, and no study pause criteria were met at any time.
NIAID 19-I- 0069	NCT03878121 / Enrolling	Negative	Max 100	IM at 500 mcg Trimer with 500 mcg Alum	Boost post Adenovirus vector prime	As of Jan 5, 2022, 12 participants have received study product. No SAEs, no SUSARs.
Therapeutic immunization study (NETI) PI: [name], Univ of Pittsburg	NCT04985760 Enrolling	Positive	24	IM at 100 or 500 mcg Trimer and 500 mcg Alum	0, 2, 5 months	As of Jan 1, 2022, 5 participants have received Trimer 4571. No related SAEs, no SUSARs.

The 5 mcg dose of 3M-052-AF adjuvant has been selected based on preclinical data and clinical experience with other recombinant HIV envelope proteins in

HVTN 137 and HVTN 300. The 500 mcg dose of Alum (ie, aluminum content by weight) adjuvant also matches the regimen in HVTN 137 and HVTN 300.

HVTN 137 has now completed enrollment in Part A and Part B. Based upon the available evidence, the HVTN 137 study team decided to proceed with a 5 mcg dose over a 1 mcg dose.

2.7 Rationale for Targeting Same Draining Lymph Node with both DNA and Protein

Direct targeting of the draining lymph node with a multipronged immune stimulus consisting of both a DNA vaccine and an adjuvanted protein vaccine leads to improved outcomes in a variety of several preclinical models (23, 29-31). The most directly relevant study is that of Felber and colleagues in rhesus macaques (31). It involved a comparison of vaccination with monomeric HIV envelope administered via both DNA and an adjuvanted protein delivered either into the same limb or into contralateral limbs, allowing for a direct comparison of 2 injections with the same regimen (protein and DNA) at the same time in the same limb versus spacing simultaneous injections into contralateral limbs. Vaccination targeting the same draining lymph nodes lead to an improvement in a variety of immune outcomes, including functional Ab responses (both increased ADCC activity and improved Fc γ RIIIa binding) and cellular responses (both CD4+ and CD8+). The proposed mechanism involves simultaneous priming of both CD4+ T cells (mostly induced by DNA) and Env-specific B cells (mainly induced by the adjuvanted protein component) in the same lymph node when injections were given in the same limb.

Most importantly, vaccination targeting the same draining lymph nodes resulted in superior protection against simian-human immunodeficiency virus (SHIV) challenge (see [Figure 2-5](#)).

[figure not shown]

Figure 2-5 Coadministration Group Shows Significant Protection from SHIV.CH505 Infection

(A) Schematic representation of vaccine delivery of the 2 components (DNA and protein) in the 2 vaccination regimens, “Coadministration” in the same anatomical sites and “separate administration” in contralateral sites. The coadministration group received DNA delivered via IM/EP followed immediately by IM injection of the adjuvanted protein. The separate administration group received the vaccine components in different anatomical sites with DNA delivered by IM/EP in the left site and protein IM in the right site. The same vaccine components and the same total vaccine dose were used for both regimens. (B) Vaccination schedule indicating the sequentially isolated CH505 immunogens used. Five weeks after the last vaccination, the animals were exposed weekly to repeated low-dose vaginal challenges using SHIV.CH505.(C) Kaplan-Meier curves show the viral acquisition rate after repeated low-dose SHIV.CH505 challenges of the two vaccine groups (n = 18 and 17, respectively) and the control group (n = 20). The RMs were exposed to 15 weekly intravaginal challenges. Infection was defined by 2 consecutive positive plasma VL measurements. No RMs were censored. P-value, exact log-rank test. Figure from Felber et al (31).

In keeping with the well-tolerated safety profile of simultaneous delivery of HIV immunogens via both DNA+ envelope protein administration strategies (32, 33),

no AEs were noted with either strategy (separate versus same draining lymph node), including assessments via clinical chemistry, complete blood counts (CBCs), body weight, temperature, and regular physical exams by veterinarians. Additionally, theoretical concerns regarding increased local reactogenicity are mitigated by the observation that the DNA vector does not disperse from the site of injection (34) and the DNA will be delivered intradermally whereas the protein will be delivered intramuscularly.

2.8 Risks and benefits

2.8.1 Potential risks

Table 2-3 Summary of potential risks of study products and administration

Risk type	Summary
Common	
 Mild to moderate injection site pain, tenderness, erythema, or swelling/induration/edema Malaise/fatigue, myalgia, or headache in the first few days following injection A vaccine-induced positive HIV antibody test result Visible lesion(s) at the injection site, such as erythematous papules with eschar, hypopigmentation, hyperpigmentation, or scar related to the EP injection
Less common	
 Severe injection site pain or tenderness Fever, chills, flu-like syndrome, arthralgia, rash, nausea, or dizziness in the first few days following injection Vasovagal reaction/lightheadedness/dizziness related to the injection procedure Transient changes in clinical laboratory values Injection site hematoma, bruising/ecchymosis, other transient lesions, itching, or bleeding related to the injection procedure
Uncommon or rare	
 Severe localized injection site reaction, such as sterile abscess or secondary bacterial infection Allergic reaction, including rash, urticaria, angioedema, bronchospasm, or anaphylaxis
Theoretical	
 Muscle damage at the injection site Electrical injury with EP Disruption of implanted electrical devices by EP Exacerbation of cardiac arrhythmia with EP Effects on a participant's response to an approved HIV vaccine administered in the future Effects on susceptibility to HIV, if the participant is exposed to HIV Effects on the course of HIV infection/disease if the participant is infected with HIV Effects on the fetus and on pregnancy

Blood drawing may cause pain, bruising, fainting, and, rarely, infection at the site where the blood is taken.

Risks during Pregnancy: Because possible effects of the study vaccine on a fetus or nursing infant are unknown, persons assigned female sex at birth who have reproductive potential will be tested for pregnancy at screening and prior to administration of each dose of study vaccine. Such persons will be asked to notify the site immediately if they suspect or learn they are pregnant during this study. In case of pregnancy, participants will continue to be followed for safety and the participant will not receive any additional vaccinations. The participant will be contacted about the outcome of a pregnancy that begins during the study.

Other Risks: The medical tests performed as part of this research protocol may result in new diagnoses or abnormal values without clinical significance (“false positives”). Depending on the medical findings and consequences of being provided with the results of these tests, the study participant may view this as either a risk or a benefit. Any such information will be shared and discussed with the participant and, if requested by the participant, may be forwarded to the primary health care provider for further workup and management.

Participants in this study risk experiencing discrimination or other personal problems that may result from study participation itself: these are known collectively as negative social impacts. The HVTN CRS is obliged to provide advocacy for and assistance to participants regarding these negative social impacts associated with the vaccine trial. If HVTN CRS staff have questions regarding ways to assist a participant dealing with a negative social impact, a designated HVTN Core representative can be contacted.

2.8.2 Benefits

Study participants will not receive direct health benefits from study participation. Others may benefit from knowledge gained in this study that may aid in the development of an HIV vaccine. The investigational vaccines are not expected to provide protection from HIV infection.

Participants may benefit from more frequent counseling, laboratory tests, and physical exams while enrolled in the study. Participants may also experience positive social impacts as a benefit of study participation. When asked, participants say that being in a study made them feel good about helping others, increased their knowledge about HIV, and improved their self-esteem.

3 Objectives and endpoints

3.1 Primary objectives and endpoints

Objectives	Endpoints
1. To evaluate the safety and tolerability of 2 doses of sD-NLT-AB05 + IL-12 DNA adjuvant followed by 2 doses of sD-NLT-AB05 + IL-12 DNA adjuvant alone or in combination with Trimer 4571 adjuvanted with 3M-052-AF + Alum	a) Local and systemic reactogenicity signs and symptoms will be collected for a minimum of 2 weeks following receipt of any study vaccine b) Serious adverse events (SAEs), medically attended adverse events (MAAEs), adverse events of special interest (AESIs) and AEs leading to early participant withdrawal or permanent discontinuation will be collected throughout the study and for 12 months following any receipt of study product. Additionally, all adverse events will be collected for 30 days after any receipt of study vaccination.
2. To evaluate the immunogenicity of 2 doses of sD-NLT-AB05 + IL-12 DNA adjuvant followed by 2 doses of sD-NLT-AB05 + IL-12 DNA adjuvant alone or in combination with Trimer 4571 adjuvanted with 3M-052-AF + Alum	a) Response rate and magnitude of vaccine-matched IgG binding Ab responses as assessed by multiplex assay 2 weeks following the fourth vaccination b) Response rate and magnitude of CD4+ and CD8+ T-cell responses measured by flow cytometry, to HIV-1-specific Env peptide pools, 2 weeks following the fourth vaccination

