9.1 Adverse events

Unsolicited AEs will be collected over a period of 30 days after each vaccination. All collected AEs are captured in the clinical database on the appropriate CRF. Clinic staff should evaluate every AE to determine if (1) the AE meets the requirements for expedited reporting (see Section 9.2.1), (2) the AE meets the criteria for a safety pause/prompt AE review (see Section 9.6), (3) the AE meets the criteria for an MAAE, and (4) the AE is a potential immune-mediated disease that may be listed as an AESI. A sample list of AESIs is provided [Appendix F](#).

In addition, a limited set of AEs will be collected and reported for 12 months following the last vaccine administration the participant receives:

- SAEs/EAEs,
- AESIs,
- MAAEs,
- AEs leading to early participant withdrawal or early discontinuation of study vaccine(s) administration.

AEs will be graded according to the DAIDS Table for Grading the Severity of Adult and Pediatric Adverse Events, Corrected Version 2.1 (<https://rsc.niaid.nih.gov/clinical-research-sites/daids-adverse-event-grading-tables>), with the following exceptions:

- Unintentional Weight Loss is required to be reported as an AE only if it is considered to be potentially deleterious to the participant's health (see HVTN 304 SSP).
- Injection Site Erythema or Redness and Injection Site Induration or Swelling will not consider surface area and interference with usual social and functional activities, such that:
 - Grade 1 is: 2.5 to < 5 cm in diameter
 - Grade 2 is: ≥ 5 to < 10 cm in diameter
 - Grade 3 is: ≥ 10 cm in diameter OR Ulceration OR Secondary infection OR Phlebitis OR Sterile abscess OR Drainage
 - Grade 4 is: Potentially life-threatening consequences (eg, abscess, exfoliative dermatitis, necrosis involving dermis or deeper tissue)

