Appendix A Schedule of procedures

Visit Number	01	02	03	04	05	06	07	08	09	10	AESI ¹³
Study Week	0	2	4	6	12	14	24	26	52	78	
Study Month	0	0.5	1	1.5	3	3.5	6	6.5	12	18	
Study Day	-56 to 1	1	15	29	43	85	99	169	183	365	547
Procedure	Screen ¹	Vac 1		Vac 2		Vac 3		Vac 4			
Study procedures											
Assessment of Understanding (AoU)		√									
Informed consent		√									
Medical history ²		√									
Physical exam ³		√	√	√	√	√	√	√	√	√	
Contraception status assessment ⁴		√	√		√	√		√			
Social impact assessment			√	√	√	√	√	√	√	√	
Social impact questionnaire						√		√		√	
Risk reduction counseling ⁵		√	√	√	√	√	√	√	√	√	
Concomitant medications ⁶		√	√	√	√	√	√	√	√	√	
Adverse Events (AEs)			√	√	√	√	√	√	√		
AESIs/MAAEs/SAEs			√	√	√	√	√	√	√	√	√
Vaccination ⁷				√		√	√				
Reactogenicity assessment ⁸				√		√	√				
EP-injection-site assessment					√	√	√	√	√	√	√
Clinical labs	Tube										
Pregnancy test (urine or serum) ^{9, 10}		√	√		√		√				
HBsAg/anti-HCV ¹⁰	SST	5									
HIV screening test ^{10, 11}	SST	5									
CBC/Differential ¹⁰	EDTA	5		5		5		5		5	
ALT & Creatinine ¹⁰	SST	5		5		5		5		5	
HIV diagnostic test	EDTA					10		10		20	
Research samples¹²											
PBMC for assays & storage	ACD	136			136	51	136		136	178.5	
Serum for assays and storage	SST	34			34	34	34		34	34	
Daily volume (mL)	190	0	10	0	180	95	180	10	180	232.5	
56-day total volume (mL)	190	190	200	200	380	275	455	10	190	232.5	

Blue shading: Vaccination Visit

¹ Screening evaluations at Visit 01 are performed no more than 56 days before Day 1.

² **Medical history:** A complete medical history is performed during screening. At enrollment and at subsequent visits, an interim medical history may be performed.

³ A complete **physical exam** is performed at screening and last clinic visit, to include height, weight, vital signs, and clinical assessments of head, ears, eyes, nose, and throat; neck, lymph nodes; heart; chest; abdomen; extremities; neurological function; and skin. At other visits, a **targeted physical exam** will be performed as needed, based on participant report or indications of illness.

⁴ **Contraception status assessment** is required only for participants who were assigned female sex at birth and are capable of becoming pregnant.

⁵ **Risk reduction counseling** per CRS Standard Operating Procedures.

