Appendix B Visit windows

Visit Number	Visit Type	Lower Allowable Window (-)	Lower Target Window (-)	Target Day*	Upper Target Window (+)	Upper Allowable Window (+)
01.0	Screening	-56	-	-	-	-
02.0	Enrollment / Vaccination 1	-	-	1	-	-
03.0	2 weeks post-vaccination 1		-4	15	+4	+7
04.0	Vaccination 2		-	29	+9	+28
05.0	2 weeks post-vaccination 2		-4	43	+4	+7
06.0	Vaccination 3		-	85	+14	+28
07.0	2 weeks post-vaccination 3	-	-4	99	+4	+7
08.0	Vaccination 4	-	-7	169	+14	+28
09.0	2 weeks post-vaccination 4	-	-4	183	+4	+7
10.0	6 months post vaccination 4	-28	-14	365	+14	+28
AESI*	Final Visit	-21	-14	547	+14	+28

All target dates are relative to Day 1, with the exception of the post-vaccination visits, visits 3, 5, 7, and 9 which are relative to the vaccination immediately preceding the visit.

*This contact must be at least 12 months post last vaccination.

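### Appendix A, as read, schedules no general AE collection from about day 14 to day 30 after vaccination 4, although primary endpoint 1b promises 30 days after every vaccination

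*Protocol*

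**What the plan says.** - **Endpoint.** Protocol Section 3.1, primary endpoint 1b: "Additionally, all adverse events will be collected for 30 days after any receipt of study vaccination".
- **Safety section.** Section 9.1: "Unsolicited AEs will be collected over a period of 30 days after each vaccination". It adds a longer, 12-month collection after the last dose for a limited set: SAEs/EAEs, AESIs, MAAEs, and AEs leading to withdrawal or discontinuation of vaccine.
- **Schedule.** In Appendix A the general AE row has seven ticks followed by two empty cells. The row for "AESIs/MAAEs/SAEs" has nine ticks and runs two columns further.
- **Timing.** In Appendix B vaccination 4 is at day 169. The visit labelled "2 weeks post-vaccination 4" is at day 183, with a target window of -4/+4 and an upper allowable limit of +7. The visit labelled "6 months post vaccination 4" is at day 365, allowable -28/+28. Target dates run from Day 1, except for "visits 3, 5, 7, and 9 which are relative to the vaccination immediately preceding the visit".
- **Other contacts.** Section 8.3 provides a symptom diary for the day of vaccination and the 14 days after it, and one contact on the third or fourth day. An interim medical history at later visits is optional (Appendix A, footnote 2).

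**The concern.** A collection period is only as good as the contacts that prompt participants to report. For doses 1 to 3, a later visit with an AE mark falls after the 30-day window has closed, so the whole window can be asked about. For dose 4 there appears to be no such visit. A site that followed Appendix A exactly would meet the schedule and still not elicit part of a primary safety endpoint.

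This is a first-in-human trial, and dose 4 is Group 2's second exposure to the adjuvanted trimer given with INO-6160. Section 6.4.3 tabulates the number and percentage of participants with each AE. With 10 per group, one participant whose only episode of an AE goes unreported moves that percentage by 1/10, or 10 points. A reader of the tables would assume equal 30-day ascertainment after every dose.

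**Working it through.** **1. Where the AE row ends.** The extracted Appendix A has lost cells, so the end of the row must be inferred.
- The AESI/MAAE/SAE row must reach the AESI contact, because Section 8.8 requires those questions there. The AE row stops two cells earlier.
- The physical exam row must reach Visit 10, because footnote 3 requires a complete exam at the last clinic visit. The AE row stops one cell earlier.
- Both comparisons put the last AE mark at Visit 09. A mark at Visit 10 would need more than one lost cell in the AE row.

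**2. The plan's own figure.** Visit 09 = 169 + 14 = day 183, as Appendix B states.

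**3. Does an AE visit fall at or after the end of each 30-day window?** Window end = dose day + 30.

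| Dose | Dose day | Window ends | First AE visit at or after the end | Lag |
|---|---|---|---|---|
| 1 | 1 | 31 | Visit 05, day 43 | 12 days |
| 2 | 29 | 59 | Visit 06, day 85 | 26 days |
| 3 | 85 | 115 | Visit 08, day 169 | 54 days |
| 4 | 169 | 199 | none | – |

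Visit 04 falls 28 days after dose 1, two days short, so it is Visit 05 that closes the first window.

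**4. Size of the gap after dose 4.** Uncovered days = 30 − (days from dose 4 to Visit 09).

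| Visit 09 timing | Days after dose 4 | Uncovered days | Share of 30 |
|---|---|---|---|
| Lower target limit, -4 | 10 | 20 | 67% |
| Target | 14 | 16 | 53% |
| Upper target limit, +4 | 18 | 12 | 40% |
| Upper allowable limit, +7 | 21 | 9 | 30% |

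The -4 is a target limit; Appendix B gives no lower allowable limit for this visit. Visit 09 is timed from the actual dose, so a late dose 4 does not shrink the gap. Even the latest allowable Visit 09 does not reach day 30.

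**5. Share of all AE windows.** Four windows of 30 days give 120 window-days, and 16/120 = 13%.

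**6. Does another contact fill it?** The diary ends at day 14 and the planned contact is at day 3 or 4. Section 8.3 continues follow-up past day 14 only for unresolved reactogenicity. Visit 10 comes 365 − 199 = 166 days after the dose 4 window closes, on target days.

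**The case against.** **The table is damaged.** The vaccination row shows three ticks for four doses, and rows have not all lost the same cell. Aligning the CBC and ALT rows from the right puts their last draw at Visit 10. Yet that visit's volume, 232.5 = 178.5 + 34 + 20 mL, leaves no room for them. This stands as a reason for moderate confidence and a check of the original page. It does not make a Visit 10 AE mark likely.

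**The duty to collect remains.** Section 9.1 still obliges sites to collect unsolicited AEs for 30 days, and Section 8.2 allows remote contact. The Study-specific Procedures, which are not among the documents, may add a prompt. This stands: what is missing is a scheduled prompt, not the requirement. A blank AE cell at day 365 is also not an error in itself, since that visit lies outside every 30-day window. The problem is that nothing earlier closes the last one.

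**Stronger readings that the documents do not support.**
- A reader might infer that about half of the last window is never asked about. SAEs, MAAEs and AESIs with onset in that interval are still scheduled for collection at Visit 10 and the AESI contact. AEs leading to withdrawal or discontinuation are kept for 12 months. MAAEs include any AE leading to an unscheduled visit to a healthcare professional.
- A reader might infer that the regimen will look better tolerated at dose 4 than at earlier doses. Section 6.4.3 plans no AE table by dose; each participant's AE is counted once, at maximum severity or strongest relationship.
- A reader might infer a distorted comparison between arms. No between-arm test of AEs is planned. The Wilcoxon test in Section 6.4.3 concerns reactogenicity, whose 14-day diary is unaffected. The gap is the same in both arms, and the dose 3 window, where the arms first differ, is covered.

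**Conclusion.** The point holds in a limited form. Sections 3.1 and 9.1 promise 30 days of general AE collection after every dose, and Appendix A, as best it can be read, provides no scheduled prompt for the later part of that window after dose 4. On target days the gap is days 15 to 30.

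The events at risk are those outside the classes kept for 12 months: non-serious, not medically attended, not AESIs and not leading to withdrawal or discontinuation. They remain recordable if volunteered. How many would be missed cannot be estimated from the documents.

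The conclusion assumes that the AE row ends at Visit 09 on the original page and that the Study-specific Procedures add no contact near day 30. Confidence is moderate for the first reason. The mismatch still deserves correction, because it touches a primary safety endpoint and is cheap to close.

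**What to change.** First confirm the AE row on the original page of Appendix A, then reconcile it with Sections 3.1 and 9.1 in one of two ways.

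- **Preferred:** add one remote AE contact at about day 30-35 after vaccination 4, as Section 8.2 permits. The cost is about 20 short contacts in total, plus a clarification memo or amendment.
- **Alternative:** mark the AE row at Visit 10 for events with onset within 30 days of vaccination 4. This adds no visit but still needs a memo or amendment, and it relies on recall more than five months after the window closes (166 days on target).

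The SAP reports that enrollment was complete by July 7, 2023, so dosing may already be finished. In that case the study report should state how days 15 to 30 after dose 4 were ascertained. The SAP covers immunogenicity only, so this statement belongs with the safety reporting.
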